## 1 SYNOPSIS

The purpose of this investigation is to determine the anti-inflammatory effect of high-dose riboflavin supplementation on chronic plaque psoriasis. Up to fifty volunteers with chronic plaque psoriasis will be recruited for a double-blind, placebo-controlled 28 week prospective study with cross-over of both the intervention and control groups at the 12 week time mark. There will be a 4 week washout period when subjects crossover. Riboflavin will be dosed 400 mg by mouth daily versus placebo. Throughout the study we will perform both clinical and laboratory assessments to measure response. Clinical assessment will include the Psoriasis-Area-and-Severity-Index (PASI), Physician Global Assessment (PGA), Dermatology -Life-Quality-Index (DLQI) and pruritus assessment will be performed at all clinical evaluations. Photographs of volunteers' skin will be taken. Skin punch biopsies of psoriasis plaques and uninvolved skin will be performed at pre-determined time points throughout the study to measure metabolomics and RNA profiling as well as histologic markers. Patients will also have regular blood draws to follow plasma measurements of riboflavin and Flavin-adenine-dinucleotide (FAD).

The primary objective is to demonstrate the superiority of riboflavin as compared to placebo at achieving a PASI 50 response (a 50% or greater improvement in PASI from baseline). Secondary objectives include, measuring the efficacy of the intervention at achieving a PGA, DLQI, or pruritus assessment score of 0/1. All statistics will be performed on a modified intent-to-treat population.

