## **6.5 Premature Withdrawal from Study**

Any subject who experiences adverse effects associated with study participation may be withdrawn from the study. Participation in the study may be discontinued for any of the following reasons:

1. Adverse events
2. Concurrent illness
3. Pain or discomfort during the study
4. Administrative reasons
5. Subject's decision to withdraw consent
6. Protocol violation.

Complete information on all adverse events will be recorded on an Adverse Event Report form (see [Appendix E – Adverse Events LOG](#) for a possible example). The Sponsor-Investigator will review all Adverse Events. The investigator will report adverse events that meet the standard IRBMED reporting guidelines (regarding relatedness and expectedness) to the University of Michigan Institutional Review Board and to the FDA as outlined in 21 CFR 312.32.

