## **7 LABORATORY ASSESSMENTS**

Biopsies will be processed for metabolomic profiling and will be taken from psoriatic normal (PN) as well as psoriatic plaque (PP) skin. Six 6 mm punch biopsies of the skin will be performed on each subject throughout the study. Two PN and two PP biopsies will be performed on week 0. Then one PN and one PP biopsy will be performed at week 12. For each subject, we will attempt to obtain all biopsies from the same plaque and the same area of normal skin. These biopsies will be divided in half and used for RNA profiling and histology.

Histological assessment will be performed for all patients using H&E, proliferation markers (Ki67), keratin 16, human beta defensin 2 (hBD2). Samples will be processed in batches of 10 patients at a time to limit batch-to-batch variation. To determine tissue responses, we will run a total of 20 patients for metabolomic and RNA-seq profiling.

All subjects will have a CBC, CMP drawn on screening and then at weeks 12, and 28. All patients in the study will have plasma measurements of riboflavin and FAD at weeks 0, 2, 12, 18, and 28. This will be a total of approximately 127 mL of whole blood per subject.

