## **8 RISK AND RISK MITIGATION**

**Title:** The Effect of Riboflavin on Moderate to Severe Plaque Type Psoriasis  
**Principal Investigator:** [name]

The risks to subjects in this study are minimal, as riboflavin is a common over-the-counter supplement and the dose in this study has been well tolerated in previous studies (see Background Information). Side effects of diarrhea and polyuria have been reported, but these resolved promptly with discontinuation of riboflavin. There have been no reported deaths. Riboflavin toxicity is unlikely and also reversed promptly by discontinuation of the vitamin.

At study visits and the close-out telephone call, all subjects will be screened for adverse events. Any reported events will be recorded on a standardized form, similar to the example included in [Appendix E – Adverse Events LOG](#). Basic labs will be drawn throughout the study, CBC and CMP, to monitor for potential toxicity to subjects' bone marrow, liver and kidneys. Pregnancy tests will be administered at each office visit to women of childbearing potential. As this dose of riboflavin has not been studied in pregnant women, any woman who becomes pregnant during the study will be discontinued.

Serious adverse events will be reported according to the UM IRB protocol in an expedited manner. These events include any untoward medical occurrence that results in: death, life threatening illness, hospitalization, persistent disability/incapacity, pregnancy, congenital anomaly/birth defect, an important medical event as deemed by the study investigators. Study investigators and staff will work together in this reporting.

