## **11 STATISTICAL METHODS**

A block randomization schedule will be created and all subjects randomly assigned to a sequence of treatment and dispensed study product. Assuming a large effect size and a conservative amount of correlation between the measurements, a sample size of 22 subjects in each sequence yields a statistical power of 80%.

All clinical and laboratory assessments will be descriptively summarized at each visit (weeks 0, 2, 12, 16, 18, and 28) for the modified intent-to-treat population. Continuous variables will be summarized with standard descriptive statistics including mean, standard deviation and range. Categorical variables will be summarized by frequency and percentage (N, %).

Differences within each sequence of treatment from baseline to endpoint will be assessed using parametric general linear models such as the paired t-test. The two sequences will also be compared with respect to dichotomized improvement from baseline to the 12-week visit for key clinical endpoints using the McNemar test. Assuming no carryover effects due to the four-week washout period, all data will be pooled and used to estimate the treatment effect. An analysis testing the assumption of equal carryover effects will be performed. Wilcoxon signed rank test will be used to compare ordinal or nominal assessments. Parametric t-tests will be used to determine if continuous laboratory assessments are significantly different between the treatment groups.

**Title:** The Effect of Riboflavin on Moderate to Severe Plaque Type Psoriasis  
**Principal Investigator:** [name]

An overall alpha-level of 0.05 will be used to determine statistical significance and all statistical tests will be two-sided. All data will be analyzed using SAS (SAS Institute, Inc., Version 9.3) software.

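### Section 11 compares the toxicity-monitoring blood tests by group-mean t-tests, which do not show how many subjects became abnormal on each treatment

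*Combined protocol and SAP*

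**What the plan says.** - **Purpose of the tests.** Section 8: "Basic labs will be drawn throughout the study, CBC and CMP, to monitor for potential toxicity", with marrow, liver and kidneys named as the organs of interest.
- **Schedule.** Section 7, headed Laboratory Assessments: "All subjects will have a CBC, CMP drawn on screening and then at weeks 12, and 28". Table 1 agrees. There is no CBC/CMP at week 0 or week 16, and Section 6.5 describes no draw at withdrawal.
- **Test.** Section 11: "Parametric t-tests will be used to determine if continuous laboratory assessments are significantly different between the treatment groups". The sentence does not distinguish CBC/CMP from plasma riboflavin/FAD.
- **Description.** Section 11: "All clinical and laboratory assessments will be descriptively summarized at each visit (weeks 0, 2, 12, 16, 18, and 28"), for the modified intent-to-treat population, and "Continuous variables will be summarized with standard descriptive statistics including mean, standard deviation and range".
- **Population.** Synopsis: "All statistics will be performed on a modified intent-to-treat population". The set is not defined, and no safety set is named.
- **Withdrawal.** Section 6.5: "Any subject who experiences adverse effects associated with study participation may be withdrawn from the study".
- **Limits.** The only numeric laboratory limits are eligibility criteria (Section 5.5.2, exclusions 8 to 10). Section 11 plans no count of abnormal values, no shift table and no adverse-event comparison.

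**The concern.** Toxicity to marrow, liver or kidney usually shows as a few subjects moving far from their own starting values, not as a shift of the whole group. A t-test asks only about the mean. A few extreme values also inflate the standard deviation in its denominator, so a gross abnormality can make significance less likely than no effect would.

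The stake is what the trial reports about safety. A statement of no significant laboratory difference between riboflavin and placebo could stand beside two or three clear abnormalities on riboflavin, visible only as the top of a range.

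**Working it through.** **Which tests are covered.** Section 7 puts CBC/CMP and riboflavin/FAD under one heading, and Section 11 gives t-tests to continuous laboratory assessments as a class. On the plain reading, CBC/CMP are included, and no other inferential method in Section 11 is directed at them.

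**The plan's own figure.** The only stated figure is 22 subjects per sequence for 80% power. Its effect size and correlation are given in words only, so it cannot be reproduced, and the point does not depend on it. It is used here only for the number of subjects: 2 × 22 = 44, each with one end-of-period CBC/CMP per treatment (weeks 12 and 28).

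**Why the size of the abnormality hardly matters.** Let k of N subjects have a within-subject difference D between treatments, and ignore noise in the rest.
- Mean difference = kD/N.
- Variance = D² × k(N − k) / [N(N − 1)].
- t = mean / √(variance/N) = √[k(N − 1)/(N − k)]. D cancels.

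With N = 44 the two-sided 5% critical value on 43 degrees of freedom is 2.02.
- k = 1: √(43/43) = 1.00
- k = 2: √(86/42) = 1.43
- k = 3: √(129/41) = 1.77
- k = 4: √(172/40) = 2.07

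In this limit four abnormal subjects are needed, however extreme each one is.

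**Simulation with noise.** The assumptions below are not from the documents: lognormal ALT with median 24 U/L, log-scale SD 0.35 between and 0.2 within subjects, 44 pairs, and k riboflavin-period values set to 200 U/L. Results of 5,000 runs:

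| k | median p | share with p<0.05 |
|---|---|---|
| 0 | – | 4.6% |
| 1 | 0.34 | 0.1% |
| 2 | 0.17 | 0.3% |
| 3 | 0.09 | 7% |

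Repeats with 2,000 to 20,000 runs gave at most 0.1% for k = 1, 0.2% to 0.5% for k = 2, and 5.9% to 7% for k = 3.

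**Other assumptions.** These runs used normal values, 20,000 runs, uncorrelated periods, and 22 or 44 values per treatment, with paired and unpaired tests. ALT had mean 25, SD 10 and an assumed upper limit of 40.
- One subject at 200: 0.1% to 1.0%.
- Two subjects at 200: 0.9% to 3.9%.
- One subject at 120: 2.1% to 3.7%.
- Two subjects at 120: 5.8% to 8.1%.
- Neutrophils (mean 4.5, SD 1.5), one subject at 0.5: 4.8% to 5.0%.

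Across these settings the test reacts to one or two abnormal subjects in between about 0% and 8% of runs, against a false-positive rate of 5%. A count against a limit shows every such subject by construction.

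**What the range adds.** It gives one highest and one lowest value per analyte and visit. It does not give the number of abnormal subjects or say whether they were normal at screening. Section 11 does not say that by-visit summaries are split by sequence. If they are not, week 12 and week 28 each mix the two treatments.

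**The case against.** **Section 11 may mean only the response laboratory tests.** The Synopsis speaks of assessments that measure response and names biopsies and riboflavin/FAD. Section 3.2 lists only riboflavin/FAD among laboratory endpoints. The summary weeks in Section 11 cover every riboflavin/FAD draw but omit screening, the only pre-treatment CBC/CMP. This reading is possible, but Section 11 does not state it and the heading of Section 7 points the other way. If it is right, the plan has no stated analysis of CBC/CMP at all, and the same fix applies.

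**Individual toxicity is watched elsewhere.** A reader might infer that the trial would miss toxicity in individual subjects. The documents do not support that. Section 8 presents CBC/CMP as monitoring, the Sponsor-Investigator reviews all adverse events (Section 6.5), serious events are reported in an expedited manner (Section 8), and the log in Appendix E records severity, seriousness and possible relation to study drug. This stands in full. It protects individuals, but it is not a comparison of treatments.

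**The modified set may contain everyone dosed.** A reader might also infer that treated subjects who stop early for adverse events are dropped from the safety tables. Because the set is undefined, that is possible but not stated. A set of all randomised subjects who took a dose would keep them.

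**A new set recovers no early laboratory data.** This is correct. A subject who stops before week 12 has no scheduled on-treatment CBC/CMP, whatever the population is called. The set would keep that subject's adverse events.

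**The exclusion limits do not transfer as written.** This is also correct. Exclusion 8 requires confirmation by a repeat test, which is not scheduled on study, and its neutrophil limit is printed as <1,5000/µL.

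**Multiplicity.** One could add that 19 unadjusted tests carry a 1 − 0.95^19 = 62% chance of at least one false signal. The documents do not list the analytes, and the figure assumes independence, so nothing here rests on it.

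**Conclusion.** The point holds as a weakness in the reported treatment comparison. As written, tests drawn to detect toxicity are compared by means, a method that reacts to one or two grossly abnormal subjects no more than marginally above chance and often well below it. Under the lognormal ALT assumptions with 44 pairs, the rate is under 1% for one or two values of 200 U/L; across all settings tried for one or two abnormal subjects it stays at or below about 8%. The exact percentages depend on assumed distributions. The closed-form result, that the size of the abnormality cancels when noise is small, does not.

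The undefined analysis set is a secondary gap: it may leave out some dosed subjects, but the documents do not say that it does. The primary endpoint is unaffected, and the documents give no ground for saying that patient monitoring is deficient.

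**What to change.** In Section 11:

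1. Restrict the t-tests to plasma riboflavin and FAD.
2. For CBC/CMP, report by treatment taken in the period ending at week 12 or week 28: the number of subjects beyond reporting limits, shifts from screening, and a listing of the values concerned. With no week 16 draw, screening is the reference for both periods.
3. Base the reporting limits on the figures in exclusions 8 to 10, applied to single values without the repeat-test condition. The sponsor must first correct the neutrophil figure. State that these limits serve tabulation only and not clinical management.
4. Add an adverse-event table by treatment, with a rule fixed in advance for events that begin in the washout.
5. Define the modified intent-to-treat set, and run the safety tables on all subjects who took at least one capsule. Say that this keeps adverse events from early withdrawals but supplies no CBC/CMP for subjects who stop before week 12.

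The cost is a paragraph of wording and two or three extra tables from data already collected. The safety laboratory tests would carry no p-values, which is a small loss.

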## 2 BACKGROUND

Psoriasis is a chronic immune-mediated skin disorder characterized by complex alterations in epidermal growth and differentiation with multiple biochemical and immunologic abnormalities. Characteristic lesions are well-demarcated, symmetrically distributed red plaques with silvery scale. In the United States, the prevalence of psoriasis is estimated to be 2% and it affects over 4 million people. Psoriasis patients suffer from reduced quality of life related to the discomfort, social stigma, and disability caused by their disease. The overall economic burden of psoriasis on the United States was recently estimated at 35.2 billion dollars with 12.2 billion dollars attributed to incremental medical costs and the rest from productivity and health-related quality of life losses. There is no cure for psoriasis and treatment is directed at controlling patients' symptoms. Current treatment options consist of topical steroids, phototherapy, topical vitamin D3 (or calcipotriol), methotrexate, and newer biologic agents.

Amongst patients with skin disease, there is significant interest in using complementary alternative medicine and vitamins to treat their disease. Some of this interest is driven by the proven efficacy of calcipotriol ointment for the treatment of psoriasis. Randomized controlled trials have shown topical calcipotriol ointment to be equivalent to a Class V topical steroid and that it has an excellent safety profile. This efficacy and safety led the United States Food and Drug Administration to approve calcipotriol ointment for psoriasis treatment in 1993 and since that time it has been an important part of psoriasis treatment.

**Title:** The Effect of Riboflavin on Moderate to Severe Plaque Type Psoriasis  
**Principal Investigator:** [name]

Given this interest in vitamin treatments and the proven efficacy of vitamin treatment for psoriasis we were intrigued when our laboratory work uncovered a significant decrease in riboflavin levels in psoriasis plaques. While measuring the metabolic profile of psoriasis plaques as compared to skin from healthy volunteers, we measured 400 fold less riboflavin in psoriatic plaques ([name], unpublished findings). Furthermore, exploring predicted drug targets using recent Genome-Wide-Association-Studies (GWAS) in psoriasis, two risk loci (*ACOX1* and *NOS2*) are targets of flavin-adenine-dinucleotide (FAD) a metabolite of riboflavin. Reviewing the medical literature, we found a number of case series from fifty to sixty years ago reporting improvement of psoriasis after riboflavin treatment. Our laboratory findings and these case reports prompted our interest in exploring the use of this vitamin to treat psoriasis.

Riboflavin, commonly known as Vitamin B2, is a water-soluble vitamin found in all living cells as mono- or dinucleotides. It is part of the Flavin family of compounds, and is the necessary precursor of the biologically important flavin adenine dinucleotide (FAD) and flavin mononucleotide (FMN). While plants and many microorganisms may generate riboflavin *de novo*, animals rely on dietary sources that they then convert to FAD and FMN. In human diets, major sources include dairy products, eggs, grains, and green leafy vegetables. Once consumed, riboflavin is absorbed via a carrier-mediated mechanism in the proximal small intestine and then excreted in the urine. Riboflavin is not stored in the body making a constant dietary supply necessary. Worldwide, Riboflavin is a bulk commodity with about 3,000 metric tons produced per year. A majority of this production is directed towards animal husbandry with a minority used for human food supplementation.

The clinical effects of riboflavin supplementation on psoriasis were first explored in the 1950s. In 1952, [name] published a case series of 148 psoriasis patients he had injected with 5-10 mg of riboflavin intramuscularly once weekly and then followed clinically. Of those 148 patients, 24% had complete remission (“healed”), and 68% had at least a 50% improvement. Only 7% of the patients failed to respond or had less than a 50% improvement. Maynard also sent surveys to 156 of his psoriasis patients that he had treated with riboflavin but whom he had not seen in clinic for two years. He received 50 survey cards back and, of those cards, 82% of patients reported they had “healed,” “improved with no relapse,” or “improved with partial relapse.” Only 18% of responders felt their disease was the same as before riboflavin treatment.

Maynard’s work was soon followed by other publications on the topic. In 1952, Sulzberger and Baer published their observations that riboflavin 30 mg by mouth daily did not help psoriasis. In contrast, in 1954, Italian investigators Montilli and Pisani reported that daily intramuscular injections of 10 mg of riboflavin either clinically cured or improved the disease in 33 out of 42 psoriasis. In 1956, [name] published a case series demonstrating that weekly intramuscular injections of 50 mg of riboflavin for 4 to 16 weeks “improved” or “markedly improved” 39 out of 44 psoriatic patients in his clinic. In contrast, in 1957, Drs. Welsh and Ede published a large case series of 348 psoriasis patients they treated with riboflavin and concluded “moderate and/or massive dosages” of riboflavin

**Title:** The Effect of Riboflavin on Moderate to Severe Plaque Type Psoriasis  
**Principal Investigator:** [name]

failed to produce any significant response in those patients. To our knowledge, there have been no more published trials or case series on the clinical effects of treating psoriasis with riboflavin. Taken together we think the results of these trials are intriguing and create clinical equipoise on whether riboflavin is an effective treatment for psoriasis.

While publications examining riboflavin and psoriasis largely stopped after the 1950s, neurologists became interested in whether riboflavin could be used to treat migraines in the 1990s. We found three human trials published on the clinical effects of riboflavin on migraine headaches involving 152 human subjects. Two of these publications included the results from randomized controlled trials and the third was an open-label study. In these reports, subjects were followed for three to six months and all subjects in the intervention groups were administered riboflavin 400 mg by mouth daily either blinded or open-label - 75 subjects total. Two of the studies observed a statistically significant and clinically meaningful improvement in the number of migraine attacks. The third study observed a statistically significant placebo effect and so found no benefit to the intervention. Interestingly, the blinded placebo in this randomized controlled trial was riboflavin 25 mg by mouth daily, so the authors wondered if even this low dose of riboflavin was biologically active. This trial was stopped prematurely, because interim analysis demonstrated the intervention would not show a statistically significant result. The authors were unable to conclude whether the results with the lower-dose of riboflavin (the “placebo group”) were an active effect or a placebo effect.

Riboflavin was well tolerated by the subjects in these studies. Only two publications included data on adverse outcomes associated with riboflavin and within these trials there were five adverse events out of the 51 patients administered riboflavin. Adverse events included diarrhea (2 subjects), upper abdominal pain, facial erythema and polyuria. One subject who experienced diarrhea withdrew early from the trial but it was reported that her symptoms resolved within 72 hours. Both studies concluded that riboflavin was safe and well-tolerated.

Finally, in ophthalmology, photoactivated riboflavin has been used for the last twelve years to treat structural deformities and inflammatory conditions of the cornea such as, keratoconus, keratectasia, and infectious keratitis. In this technique the corneal epithelium is removed, riboflavin is applied and the tissue is irradiated with ultraviolet A light. The riboflavin strengthens the collagen in the cornea and biochemically stabilizes the layer to prevent further complications from these conditions.

In conclusion, psoriasis is a common and socially stigmatizing condition in the United States. Our laboratory metabolomics profiling has shown that psoriasis plaques have significantly less riboflavin than healthy controls. Previous human case reports suggest that riboflavin is clinically effective for the treatment of psoriasis; however, they were not conclusive. More recent human trials have shown that 400 mg of daily oral riboflavin is a safe and well-tolerated medication to administer to humans. Our laboratory data, the published case reports of riboflavin’s effectiveness and its safety led us to propose these clinical and laboratory experiments to better determine riboflavin’s effects on psoriasis.

